**Evaluating Public Health Interventions to Improve COVID-19 Testing Among
Underserved Populations**

PROTOCOL; STATISTICAL ANALYSIS; INFORMED CONSENT FORM

NCT05270694

07 November 2024

PROTOCOL

Using a community-based approach, we engaged participants from vulnerable communities in a cohort study focused on at-home COVID-19 testing. Participants received in-person instruction on testing and were provided with at-home COVID-19 test kits while answering monthly surveys on testing use and behavioral factors. By following a community engaged model we aimed to build trust and understanding in order to engage these vulnerable communities both effectively and ethically.

Setting and Participants

We conducted a longitudinal cohort study of at-home COVID-19 testing from March 2022 - November 2023, with recruitment focused on Portland, Maine. We aimed to engage a roughly equal number of participants from the immigrant, housing unstable, and low-income/uninsured communities. Individuals were eligible to participate if they were aged ≥ 18 years and either: 1) an immigrant; 2) currently unhoused or had a history of chronic homelessness; or 3) received services through Portland Public Health (specifically the Portland Community Free Clinic [PCFC], Sexually Transmitted Disease [STD] Clinic, or Needle Exchange). The MaineHealth Institutional Review Board approved the protocol.

Intervention

All participants attended an individual in-person enrollment session with research staff in which they were consented, learned to perform a COVID-19 test, completed a baseline survey, and received five at-home COVID-19 tests. Participants then received five at-home COVID-19 tests every eight weeks for 48 weeks (30 tests total), regardless of whether they used all previous tests; this constituted the “testing program.” Participants received their test kits either by mail or in-person at community partner sites or another location selected by the participant to ensure accessibility.

Measures

The baseline survey included study-specific questions regarding COVID-19 test use and behavioral factors (i.e. risk perceptions, attitudes, norms), as well as the RADx-UP Common Data Elements (CDEs), a set of standardized questions used in National Institutes of Health (NIH) funded COVID-19 research to build a repository of COVID-19 data (details of the CDE are shown in Appendix A). Participants then completed a brief survey every four weeks on COVID-19 exposures, symptoms, and their use of COVID-19 tests. Every eight weeks participants completed a longer survey that included additional questions on behavioral factors around COVID-19 testing. The initial eight-week survey also included questions adapted from the validated National Institute on Drug Abuse (NIDA)-Modified ASSIST survey regarding substance use behaviors. In total, each participant completed one baseline and twelve follow-up surveys over the span of 11 months.

NIH translation services translated all recruitment and survey materials into seven languages (Somali, Arabic, French, Kinyarwanda, Lingala, Portuguese and Spanish) representing the top languages spoken by patients of GPH. We securely hosted and stored the surveys on a REDCap database, and distributed the REDCap survey link to participants over email, text, or WhatsApp. If requested, research staff also administered the surveys over the phone or in-person. Participants who did not respond to a survey were sent a reminder email/message up to three times over six days; on day seven they were called by research staff. Participants were considered lost to follow-up if they missed completing three consecutive surveys and could not be reached. Participants

could receive up to \$250 in grocery gift cards for their participation in the study: a \$50 gift card at enrollment, \$20 gift cards every eight weeks for completing surveys, and \$40 gift cards for reaching the half-way point and end of the study.

The primary outcome was “desired testing behavior score.” In every survey, participants were asked whether, in the last month, they had a close contact exposure to a known case of COVID-19 or experienced symptoms concerning for COVID-19 (reporting yes/no to a list of twelve symptoms), indicating an instance where testing was CDC recommended. Following these questions, participants were then asked if, in the last month, they had taken a COVID-19 test. The “desired testing behavior score” was then calculated as the proportion of surveys in which a participant reported taking a COVID-19 test when they reported an indication to test. For example, if a participant reported a symptom and/or exposure in five of their surveys but only reported testing in three of those surveys, then their desired testing behavior score was 3/5, or 0.6.

Independent variables examined in the analysis included vulnerability groups, behavioral factors, and demographic variables. The four dichotomous vulnerability groupings included: 1) immigrants 2) unhoused or history of chronic homelessness 3) low-income and/or uninsured and 4) substance use. We also calculated a “vulnerability score” for each participant indicating the number of vulnerabilities each participant identified with. The five behavioral factor scores related to COVID-19 testing and illness, measured using 5-point Likert scale questions, were: 1) confidence in ability to use tests 2) perceived severity of illness from COVID-19 3) perceived usefulness of testing 4) norms around testing and 5) commitment to testing. Additionally, we analyzed seven demographic characteristics: age, sex, race, employment status, education level, COVID-19 vaccination status, and self-reported health status.

STATISTICAL ANALYSIS

We performed a descriptive analysis to characterize demographics and vulnerability status of the participants. We also stratified by vulnerability group to describe differences across groups. We examined whether COVID-19 testing behavioral factors differed by vulnerability group by using two-sample t-tests to perform difference testing between group and non-group for each behavioral factor score.

We performed bivariate linear regressions to assess the association between desired testing behavior and each vulnerability, behavioral, and demographic factor. Factors significantly associated with desired testing behavior in the bivariate regressions were then included in a multivariate linear regression; the vulnerability score was also included, despite non-significance in bivariate analysis, as the previous literature and earlier qualitative analysis in our community indicated these categories have a strong relationship with testing. A linear relationship was confirmed by a plot of residuals against the predicted values. There was no evidence of multicollinearity, as assessed by tolerance values > 0.1 and VIF values < 10 . The assumption of normality was met, as assessed by visual inspection of the Q-Q plot. Analyses were conducted using STATA version 17.0.

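### Test use is asked at baseline but enters no regression, so associations between attitudes and the testing score may partly reflect prior testing habit

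*Combined protocol and SAP*

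**What the plan says.** Protocol, Measures, on what is collected at enrolment: "The baseline survey included study-specific questions regarding COVID-19 test use and behavioral factors". The wording and recall period of the baseline test-use questions are not given.

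The same section gives the predictors: "Independent variables examined in the analysis included vulnerability groups, behavioral factors, and demographic variables". These are four vulnerability groupings with a count of them, five behavioural scores, and seven demographic items ("age, sex, race, employment status, education level, COVID-19 vaccination status, and self-reported health status"). Testing before the programme is in none of the three families.

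The outcome is a per-participant score, "calculated as the proportion of surveys in which a participant reported taking a COVID-19 test when they reported an indication to test". On the questions that feed it: "In every survey, participants were asked whether, in the last month, they had a close contact exposure to a known case of COVID-19". The schedule is that "each participant completed one baseline and twelve follow-up surveys over the span of 11 months".

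Statistical Analysis runs one bivariate regression per listed factor and then applies this rule: "Factors significantly associated with desired testing behavior in the bivariate regressions were then included in a multivariate linear regression". The only exception is the vulnerability score, which is forced in.

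**The concern.** This is a single observational cohort (Setting and Participants), so the covariates are the plan's only protection against confounding. Confidence, perceived usefulness, norms and commitment are attitudes that people who already test are likely to hold, and those people are also likely to keep testing. With prior testing absent from the model, its contribution is credited to the attitude. Measuring attitudes at baseline and testing later would not cure this, because the habit comes before both.

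At stake is how the multivariable model is read. A reader will take a significant attitude as related to testing over and above the other factors, when it may partly mark people who would have tested anyway. The item needed to examine this appears to be in the data already, and the plan gives no reason for leaving it out.

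**Working it through.** **1. Route into the model.** Candidates are the 4 groupings and their count, 5 behavioural scores and 7 demographics. Only these are screened, and only those that pass, plus the vulnerability score, are fitted together. Baseline test use is not a candidate, so it cannot enter at either step.

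**2. No design figure to reproduce.** The documents give no sample size, standard deviation, correlation or effect size. All inputs below are assumptions.

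**3. Confounding, closed form.** On standardised variables, let x be an attitude with no effect of its own, w prior test use, r their correlation and b the coefficient of w. Omitting w gives x a coefficient of b × r, with standard error √[(1 − (b·r)²)/(n − 2)]. At n = 200:

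- r = 0.3, b = 0.3: coefficient 0.09; p<0.05 in 25% of samples
- r = 0.3, b = 0.5: coefficient 0.15; 57%
- r = 0.5, b = 0.5: coefficient 0.25; 95%

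At n = 100 the three rates are 15%, 32% and 72%. The nominal rate is 5%.

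**4. Confounding, simulated on the score itself.** Assumptions: n = 200, about 4 indicated surveys each, a latent habit that raises the log-odds of testing, an attitude correlated with habit but without its own effect, and HC3 standard errors. Share of samples with p<0.05 for the attitude:

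| Correlation with habit; log-odds per SD of habit | Unadjusted | Adjusted: any test plus capped count | Adjusted: yes/no item only |
|---|---|---|---|
| 0.4; 0.8 | 89% | 51% | 72% to 81% |
| 0.3; 0.5 | 39% | 26% | 32% |
| 0.1; 0.3 | 6% | little to remove | little to remove |

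The adjusted rates depend on how closely the baseline item tracks habit. A more informative item brought the first two rows to 30% and 12%. The only test-use question the documents describe is whether a test was taken in the last month, which is nearer to the yes/no column.

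**5. Precision.** The variance of the attitude coefficient, adjusted over unadjusted, is (1 − partial r² of w with the outcome)/(1 − r²). It is below 1 only if the partial correlation of w with the outcome exceeds its correlation with the attitude. With a true attitude coefficient of 0.20, the standard-error ratio runs from 0.86 (r = 0, b = 0.5) to 1.15 (r = 0.5, b = 0.1). In the simulated strong case it did not move (0.0217 against 0.0218), although R² rose from 0.05 to 0.16. Only a factor unrelated to habit gained: 0.0227 to 0.0214, and (0.0227 − 0.0214)/0.0227 is about 6%.

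**6. Baseline on both sides.** The outcome questions were asked in every survey, and the count is 1 + 12 = 13 with baseline included. If baseline is scored, an indicated baseline survey has weight 1/k among k indicated surveys: 1.0 at k = 1, 0.20 at k = 5, 0.077 at k = 13. In simulation with no habit at all, baseline testing still correlated 0.11 to 0.21 with such a score (indication rate 0.2 to 0.6 per survey, testing probability 0.5). Baseline test use can therefore be a covariate only for a score built without the baseline survey.

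**The case against.** Three arguments have weight.

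*The plan claims association only.* A bivariate association is not wrong because a third variable explains part of it. This stands for the bivariate regressions, which should stay as planned. It is weaker for the multivariable model, whose purpose is to separate factors.

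*The causal direction is assumed.* Attitudes may have led to the earlier testing. Prior testing would then lie on the pathway, and adjusting for it would remove part of the association of interest. This stands, and it is why the adjusted estimate should sit beside the unadjusted one and not replace it.

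*The size is assumed, and the baseline item is unseen.* This also stands. With weak links the false-positive rate is about 6% and there is almost nothing to fix; with a yes/no item most of the excess survives adjustment.

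A reader might also infer that leaving out a strong predictor costs precision across the board. The documents do not support this. That reasoning belongs to randomised comparisons, where the covariate is unrelated to the factor of interest. Here the concern itself presumes a correlation between the two, and the standard error may stay the same or rise.

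**Conclusion.** The omission is real: test use is asked at baseline, no regression uses it, and no reason is given. Prior testing is a plausible and unaddressed confounder of confidence, usefulness, norms and commitment. In the simulated cases at n = 200, a null attitude is significant in about 6% to about 89% of samples, and adjustment removes only part of the excess. These figures rest on assumed sample size, correlations and item quality, so they show what is possible and do not estimate what happened in this cohort.

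The documents do not support reading the reported attitude associations as spurious, since neither the strength nor the direction of the links is known. The point is a cheap improvement to the multivariable analysis. It does not invalidate the plan.

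**What to change.** 1. Keep the bivariate regressions as planned.
2. In the multivariable model, add baseline test use in whatever form it was collected, entered outside the bivariate screen.
3. For this analysis, build the score from the twelve follow-up surveys only, and state whether the baseline survey counts in the main score.
4. Report behavioural-factor and vulnerability estimates with and without baseline test use, on the same participants and the same score, noting that it may be a confounder or lie on the pathway.
5. Statistical Analysis already reports a bivariate result (the vulnerability score was not significant), so label this as an added analysis. If the item proves unusable, say why and list the omission as a limitation.

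Cost: one or two covariates that appear to be already collected, a re-scored outcome and a re-run. Participants whose only indication was at baseline drop out of these models, and residual confounding remains because a baseline item measures habit imperfectly.

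### Does an unstated scoring window let the pre-program baseline survey distort the desired testing behavior score?

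*Combined protocol and SAP*

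**What the plan says.** The Measures section introduces the primary outcome with the indication items: "In every survey, participants were asked whether, in the last month, they had a close contact exposure to a known case of COVID-19". A symptom list and a question on having taken a test follow, also covering the last month. The score is then "calculated as the proportion of surveys in which a participant reported taking a COVID-19 test when they reported an indication to test", with a worked example of 3/5 = 0.6. No first survey and no exclusion is given, and the Statistical Analysis section adds none.

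Three other statements bear on whether baseline belongs in that proportion:

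- **Timing.** Under Intervention, participants at the enrollment session "learned to perform a COVID-19 test, completed a baseline survey, and received five at-home COVID-19 tests".
- **Count.** Under Measures, "each participant completed one baseline and twelve follow-up surveys over the span of 11 months", so baseline is called a survey.
- **Content.** Also under Measures, "The baseline survey included study-specific questions regarding COVID-19 test use and behavioral factors", together with the RADx-UP common data elements. The next survey is described differently: "Participants then completed a brief survey every four weeks on COVID-19 exposures, symptoms, and their use of COVID-19 tests".

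**The concern.** If the indication and testing items were asked at every survey, and baseline is a survey, the stated rule mixes one month without the program's training or kits with up to twelve program months. The score is the dependent variable in every regression in the Statistical Analysis section.

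Two things would be at stake. A participant with few indications could have a score resting largely or wholly on the pre-program month. And follow-up length varies ("Participants were considered lost to follow-up if they missed completing three consecutive surveys and could not be reached"), so baseline would weigh more in a group that drops out earlier. Groups with identical behavior could then appear to differ.

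**Working it through.** **1. The plan's own figure.** Three tested surveys out of five indicated gives 3/5 = 0.6, as stated. If one of the five is baseline and is removed, the score becomes 3/4 = 0.75 (baseline month untested) or 2/4 = 0.50 (tested). With two indicated surveys, one of them baseline, a score of 0.5 becomes 1.0 or 0.0. If baseline is the only indicated survey, the score is undefined without it. Individual scores can therefore move a good deal.

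**2. Was baseline eligible?** The outcome paragraph points to yes. The survey descriptions point the other way: test use is listed for baseline, but exposures and symptoms are named only for the four-weekly surveys. The common data elements might contain such items, but their appendix is not in the text available here. The documents do not settle the question.

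**3. Average weight if baseline was scored.** The documents give no rates. Assume one indication rate q in every survey, independent across surveys, with K follow-ups completed. By symmetry each of the K + 1 surveys carries average weight 1/(K + 1): 1/13 = 7.7% for K = 12, 1/7 = 14.3% for K = 6 and 1/4 = 25% for K = 3. With testing probabilities p0 before and p1 during the program, the mean score is p0/(K + 1) + p1·K/(K + 1), whatever q is.

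Large individual weights are consistent with this. For K = 12:

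| | q = 0.1 | q = 0.2 | q = 0.3 |
|---|---|---|---|
| Scored participants indicated at baseline, q/(1 - (1 - q)^13) | 13.4% | 21.2% | 30.3% |
| Average share of their score due to baseline | 57.4% | 36.3% | 25.4% |
| Product | 7.7% | 7.7% | 7.7% |

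**4. Shift in a group contrast, full follow-up.** With baseline the contrast is d0/13 + 12·d1/13; without it, d1. The difference is (d0 - d1)/13.

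- d0 = d1: 0.
- 20 points falling to 10: 10/13 = 0.77 points.
- 10, 20 or 30 points falling to zero: 0.77, 1.54 or 2.31 points.

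**5. Unequal dropout, identical behavior.** Assume 30% of one group and 10% of the other stop after three follow-ups, with p0 = 0.4 and p1 = 0.6. Mean scores are (0.4 + 12 × 0.6)/13 = 0.585 for completers and (0.4 + 3 × 0.6)/4 = 0.550 for those who stop, a difference of 0.0346 before rounding. At q = 0.2 a score exists for 94.5% of completers and 59.0% of those who stop. Early stoppers are then 0.3 × 0.590/(0.3 × 0.590 + 0.7 × 0.945) = 21.1% of the scored in one group and 0.1 × 0.590/(0.1 × 0.590 + 0.9 × 0.945) = 6.5% in the other. The spurious gap is (0.211 - 0.065) × 0.0346 = 0.0051, or 0.51 points. Across q = 0.1, 0.2 and 0.3:

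| Stop after | p0 to p1 | Spurious gap (points) |
|---|---|---|
| 3 follow-ups | 0.4 to 0.6 | 0.40, 0.51, 0.58 |
| 3 follow-ups | 0.3 to 0.7 | 0.80, 1.01, 1.17 |
| 6 follow-ups | 0.4 to 0.6 | 0.21, 0.24, 0.25 |
| 6 follow-ups | 0.3 to 0.7 | 0.42, 0.47, 0.50 |

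**6. What follow-up-only scoring would cost.** Participants indicated only at baseline lose their score. As a share of defined scores this is q(1 - q)^K/(1 - (1 - q)^(K + 1)). For q = 0.1, 0.2 and 0.3 it is 3.8%, 1.5% and 0.4% with full follow-up, but 21%, 17% and 14% among those who stop after three. The loss falls mostly on the participants with least follow-up.

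**The case for a change.** The best case for a change is that a primary outcome should be reproducible from its definition, and this one is not quite. Two analysts could include or omit baseline and obtain different scores, and even different analysis sets, from the same data. The opening paragraph can also be read as tying the surveys to the program, since participants "were provided with at-home COVID-19 test kits while answering monthly surveys on testing use and behavioral factors". The data are in hand, so restricting the score to the twelve follow-ups looks cheap.

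The gap in the text is real, and that part stands. The step to a changed definition does not. The opening paragraph is a general description, not a scoring window. The score is defined as testing when an indication was reported, by any test and not only a program kit, so a baseline month measures the same behavior. The regressions relate the score to participant characteristics within one cohort; there is no before-after or between-arm effect for a pre-program month to contaminate. Finally, the document reports completed work: surveys ran from March 2022 to November 2023, and the Statistical Analysis section already mentions a non-significant bivariate result. If baseline was counted, redefining the primary outcome now would be a choice made with results known, and it would bring the uneven loss in step 6.

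**Conclusion.** No change to the plan. The documents leave open whether baseline enters the score, and harm requires two unconfirmed facts: that baseline carried the exposure and symptom items, and that it was counted. If the items were absent, the reference to every survey is loose wording for every follow-up survey and nothing was mixed. If they were present and counted, the effect on a group contrast is zero when the gap is the same before and during the program, 0.77 points when a 20-point gap halves, and at most 2.3 points in the scenarios tried. The dropout scenarios give 0.2 to 1.2 points.

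These sizes assume equal, independent indication rates across surveys, with testing and dropout rates chosen for illustration. They cover group contrasts; the coefficients of the behavioral factors were not computed. A baseline indication rate well above the follow-up rate would raise baseline's weight. Within those limits the planned associations stay essentially sound. Which surveys were counted is a detail that the analysts know and would ordinarily state when reporting the score.

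### The primary outcome counts every survey with a symptom or exposure as a separate indication, so a continuing symptom or an illness spanning a survey date can enter the denominator more than once

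*Combined protocol and SAP*

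**What the plan says.** The primary outcome is defined in the protocol's Measures section. On exposure: "In every survey, participants were asked whether, in the last month, they had a close contact exposure to a known case of COVID-19". The symptom part of the indication is that the participant "experienced symptoms concerning for COVID-19 (reporting yes/no to a list of twelve symptoms), indicating an instance where testing was CDC recommended". On testing: "participants were then asked if, in the last month, they had taken a COVID-19 test".

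The score is the "proportion of surveys in which a participant reported taking a COVID-19 test when they reported an indication to test". The worked example begins "if a participant reported a symptom and/or exposure in five of their surveys but only reported testing in three of those surveys" and arrives at 0.6. It confirms that the survey is the unit of counting and that one symptom or one exposure is enough.

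On timing, the same section says "Participants then completed a brief survey every four weeks on COVID-19 exposures, symptoms, and their use of COVID-19 tests", and that "each participant completed one baseline and twelve follow-up surveys over the span of 11 months".

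Nothing in the document requires a symptom to be new or worse than usual, treats consecutive positive surveys as one episode, or carries a test over to the next survey. The STATISTICAL ANALYSIS section regresses the score linearly on each vulnerability, behavioral and demographic factor. The demographic factors are "age, sex, race, employment status, education level, COVID-19 vaccination status, and self-reported health status". Apart from the vulnerability score, which was retained regardless, statistical significance in these single-factor models decides what enters the multivariable model.

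**The concern.** The denominator can grow without any new occasion to test. There are two routes.

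- **Date crossing.** An illness that begins before one survey and ends after it can be reported at both. One test at onset is then usually scored 1/2.
- **Lasting symptom.** A symptom present every month makes every survey an indication. A person who tests at each new illness, but not each month for the continuing symptom, scores low.

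The second route matters most for inference. Lasting symptoms may plausibly be more common with poorer self-reported health, older age, substance use or unstable housing, and all of these are examined as predictors of the score. Two groups that respond identically to new illness could then differ on the score, and the difference could be read as a barrier to testing. Because single-factor significance governs selection, it could also affect which factors reach the multivariable model. The checks described (residual plot, Q-Q plot, tolerance and VIF) would not reveal it.

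**Working it through.** **1. The plan's own figure.** Score = (surveys with indication and test) / (surveys with indication) = 3/5 = 0.6, as stated.

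**2. Inputs.** From Measures: surveys four weeks (28 days) apart, 12 follow-up surveys plus baseline. Assumed, because the document does not give them: illness duration, number of illnesses, share of people with a lasting symptom, and how often people test without a new illness.

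**3. One person with a lasting symptom.** With *k* new illnesses in separate survey periods, all tested, and no other testing, the score is *k*/12. For *k* = 1, 2, 3, 4 this is 0.083, 0.167, 0.25, 0.333. With baseline counted (*k*/13) it is 0.077, 0.154, 0.231, 0.308. Counted per new illness it would be 1.0 each time.

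This depends on testing in the other months. With *k* = 2 and a test in a share *q* of the 10 symptom-only months, the score is (2 + 10*q*)/12: 0.167, 0.375, 0.583 and 1.0 for *q* = 0, 0.25, 0.5 and 1.

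**4. One short illness, tested once at onset.** If onset is uniform over the 28-day cycle, an illness of *L* days crosses a survey date with probability *L*/28. The mean score is 1 − 0.5 × *L*/28.

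| *L* (days) | P(crosses) | Mean score |
|---|---|---|
| 5 | 0.18 | 0.91 |
| 7 | 0.25 | 0.875 |
| 10 | 0.36 | 0.82 |
| 14 | 0.50 | 0.75 |

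**5. Population simulation.** 200,000 persons, 13 survey periods, onset probability 3/13 per period, a test in the onset period with probability 0.8, and carry-over to the next period with probability *L*/28. With no other testing, the mean score is 0.80 (no carry-over), 0.73 (5 days), 0.66 (10 days) and 0.61 (14 days). With a permanent symptom it is (3/13) × 0.8 = 0.185.

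**6. Spurious group gap.** Both groups behave identically and differ only in the share with a permanent symptom. Illnesses last 10 days. Gap = (difference in shares) × (score without − score with a permanent symptom). Background testing occurs in a share *q* of all periods, so the permanent-symptom score is 0.185 + 0.815*q*.

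| *q* | Score without | Score with | Gap, 30% v 10% | Gap, 15% v 10% |
|---|---|---|---|---|
| 0 | 0.66 | 0.18 | 0.095 | 0.024 |
| 0.25 | 0.74 | 0.39 | 0.071 | 0.018 |
| 0.5 | 0.83 | 0.59 | 0.047 | 0.012 |

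First row: 0.20 × (0.659 − 0.185) = 0.095 and 0.05 × 0.474 = 0.024.

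**The case against.** - **The item wording is not available.** The twelve symptoms and the question stem are not in the text supplied. A participant may not report a known, explained symptom as one that raises concern for COVID-19. This stands: if the items asked about new symptoms, most of the lasting-symptom effect disappears. What can be said is that the protocol does not state such a condition.
- **People could test every month.** The Intervention section supplies 30 tests, and any test in the month earns credit. A reader might infer that anyone with lasting symptoms must score low. The documents do not support that: the low score requires little testing in continuing-symptom months, and the gap roughly halves at 50% background testing.
- **Date crossing does not by itself create a false predictor.** It is a matter of calendar timing, lowers scores generally, and yields no group contrast unless illness duration differs by group. This also stands. The false-barrier argument rests on unequal lasting symptoms, for which the documents give no data.
- **The definition is open and is a legitimate choice.** A symptomatic month without a test is scored correctly under the rule as written. That is a reason to keep the score as primary. It does not show that an association with the score reflects response to new illness.
- **The vulnerability score was non-significant in the single-factor analysis.** So no artefact surfaced for that summary measure. This does not settle the individual groups, self-reported health or age.

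**Conclusion.** The written rule allows one continuing symptom or one illness to be counted at more than one survey, and nothing in the document offsets this. For an individual the effect can be large (0.25 instead of 1.0 in the example). For a group contrast it ranges from about 0.01 to about 0.095 under the assumptions shown: 10-day illnesses, three expected illnesses, 80% tested at onset, lasting-symptom shares of 15% or 30% v 10%, and background testing from 0 to 50% of periods. The upper figure is the no-background-testing end of that range.

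A reader might infer that the study's associations with health, age, substance use or housing are artefacts. The documents do not support that. They show neither how common lasting symptoms were, nor whether they differed by group, nor the exact question asked. The supported conclusion is that the primary regressions are open to a plausible bias of uncertain size, which can be examined cheaply with answers already collected.

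**What to change.** Keep the original score as primary. State the symptom-item wording, including whether symptoms had to be new. Then add two sensitivity analyses on the existing data:

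1. **New-episode score.** Count a run of consecutive surveys that report the same symptom or symptoms, with no newly reported symptom and no exposure, as one indication. Credit it if a test is reported at the onset survey or the next one. Allowing the next survey matters: with an assumed two-day delay to testing, about 2/28 = 7% of onsets would have their test fall after the survey date and lose credit. State a rule for baseline (for example, treat as new, or exclude) and for a missed preceding survey (for example, compare with the last completed survey, or exclude).
2. **Split score.** Compute the original score separately for surveys with an exposure and surveys with symptoms only.

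Repeat the regressions on each and report estimates with confidence intervals beside the original. Describe any factor whose association changes materially as sensitive to the definition of an indication. Agreement in direction alone is too weak a rule, because it ignores size and precision.

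**Cost.** Recoding and a few extra sets of regressions, with no new data. There will be fewer indications per person. Exposure carry-over and intermittent chronic symptoms are not fully removed, a new illness showing only an already-present symptom is missed, and crediting the next survey may count some unrelated tests.
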